**Study Implementation and Data Security.** We will take careful precautions to maintain confidentiality for all participants, using procedures we have used with similar previous studies: All research personnel will attend a required in-service training conducted by the PI where the screening, informed consent, and assessment protocols will be described. All members of the research team will sign a confidentiality agreement that no identifying information of specific individuals will appear in any external documents (e.g., peer-reviewed publications, presentations) or in any internal reports.

All study data related to study outcomes (i.e., urine drug screens, participant responses to questionnaires and interviews, EMA data, geolocation) and demographics will not have any unique identifying data attached in any way. All participants will be assigned a numerical study identifier to minimize the potential to link identifying information with study data. One master list of study participants will be kept separate from all other study data. The master list will be destroyed upon study completion; it will be kept separate from all data and will be available only to the PI, Study Coordinator, and research assistants. To protect participant confidentiality, all data will be maintained in a manner consistent with IRB-approved protocol. Data will be entered directly into RedCap wherever possible. If paper data is necessary, it will be stored in locked filing cabinets within a locked office and on MUSC's encrypted computers and data servers. Access to de-identified study data will be limited to named project investigators, the Study Coordinator, NIH audit personnel and MUSC IRB audit personnel. Data will be maintained per IRB-approved protocol.

The study protocol and safety plan will be printed and kept in a central location within the research space for easy access, and on the MUSC server. Standard operating procedures (SOPs) for the management of any participant or study-related emergency will be established and research staff will be trained on these protocols. All participant assessments will be scheduled during normal working hours on the MUSC campus or remotely to ensure clinical staff are reachable and the safety of participants and research staff is maintained. After-hours appointments will be scheduled in advance and study staff will ensure clinical staff and/or PI are on call for any after-hours appointments.

All research staff has completed or will complete the University of Miami CITI training course in the responsible conduct of research. Necessary certifications in the responsible conduct of research and the protection of human research participants will be completed on an annual basis, in compliance with MUSC institutional and NIH regulations.

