**Table 1. Eligibility Screening and Baseline Assessment Measures**

Instrument	Purpose	BSL	Exit	Daily
Breathalyzer Test	Screen for alcohol	X		
Urine Drug Test	Screen for drug use	X		
Pregnancy Test	Screen for pregnancy	X		
Breathalyzer Policy	Required document	X		
Participant Locator Form	Required document	X	X	
Participant Contact Form	Collect contact information	X		
Demographics Form	Collect demographics	X		
Participant History Form	Collect medical history and medications	X		
Adverse Events Form	Collect adverse Events		X	
EMA Morning Report	Collect daily substance use, partner conflict, mood and affect, device accessibility			X
EMA Random Report	Collect daily substance use, partner conflict, mood and affect, device accessibility			X
CIWA-Ar	Assess alcohol withdraw	X		
Mini Mental Status Exam (MMSE) 	Screen for cognitive deficits	X		
QuickSCID 	DSM-5 psychiatric disorders	X		
Traumatic Life Events Questionnaire (TLEQ) 	Assess trauma history	X		
Time Line Follow-Back 	Alcohol and drug use, IPV	X	X	
PTSD Checklist (PCL-5) 	Assess PTSD symptoms	X		
Beck Depression Inventory-II (BDI-II) 	Assess depression	X		
Alcohol Use Disorders Identification Test 	Alcohol problem severity	X		
Fagerstrom Test for Nicotine Dependence (FTND) 	Assess nicotine use	X		
Comprehensive Effects of Alcohol Questionnaire 	Alcohol expectancies	X		
Drinking Motives Questionnaire-Revised 	Drinking motives	X		
Revised Conflict Tactics Scale 	Intimate partner violence	X	X	
Dyadic Adjustment Scale-short form 	Relationship functioning	X	X	
State-Trait Anger Expression Inventory 	Trait anger	X		
Dissipation-Rumination Scale 	Hostile rumination	X		
Difficulties in Emotion Regulation Scale (DERS)	Assess Emotion Regulation	X		
Urgency, Premeditation, Perseverance, Sensation Seeking, Positive Urgency Impulsive Behavior Scale (UPPS-P)	Measure impulsivity	X		

HRV4Biofeedback Survey	Measure emotional state before and after breathing exercise during last 7 days			X
Breathing Prompt	Prompt breathing exercise during last 7 days			X
Website Analysis and Measurement Inventory 	Feasibility and Acceptability		X	
Post-Study System Usability Questionnaire 	Usability		X	
Client Satisfaction Questionnaire 	Client satisfaction		X	

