**HRV-B Implementation.** Participants will be trained at baseline and then will be randomly prompted once daily on days 22-28 to complete 10 minutes of HRV-B according to published protocol. Participants will also be able to use HRV-B more often if they choose. HRV-B will guide participants in an evidence-based paced breathing technique (about 6 breaths per minute) using visualization on their mobile device of their real-time cardiac parameters. This process can reduce sympathetic dominance, enhance autonomic stability, and affect regulation, which cannot be accomplished by alternatives such as relaxation or deep breathing because participants must learn to breathe at their individualized cardiovascular resonant frequency.

**HRV-B Usability, Feasibility, and Acceptability.** We will assess the number of started, incomplete, and completed HRV-B sessions. Participants will be prompted twice at random intervals to respond to a brief survey assessing HRV-B: 1) ease of use, 2) willingness to continue use, 3) perceived helpfulness, 4) patient satisfaction, and 5) suggestions for modifications. In addition to providing subjective usability, feasibility, and acceptability at the exit interview, participants will complete the Website Analysis and Measurement Inventory (WAMMI), Post-Study System Usability Questionnaire (PSSUQ), and 8-item Client Satisfaction Questionnaire (CSQ). The investigators will discuss these outcomes and integrate participant suggestions for our planned R01 application.

**Compensation.** Participants will receive \$50 for the baseline assessment, \$1 per completed EMA report (\$112 maximum), a \$10 bonus for each week in which ≥80% of EMA reports are completed (\$40 maximum), \$10 for the purchase of the HRV4Biofeedback app, \$25 for completing all 4 weeks of participation, and \$25 for returning borrowed equipment (*return mailers provided*) for a possible \$252 total. Participants will be compensated via Clincard, or with check or cash.

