**C. Potential Risks**

Confidentiality: Breach of confidentiality is associated with all research that is not anonymous. Realization of this risk could cause negative social or legal consequences. Given that data will be linked to participants' identity between completion of the telephone screening interview and completion of the final assessment, this is an important risk to consider. We believe that the risk is very low, given that most data are collected electronically and all data will be stored securely and separately from identifying data. Several safeguards and procedures for protecting data will be in place (see Adequacy of Protection Against Risks below). All possible efforts to protect participants' privacy and confidentiality will be made throughout the course of the study. Participants will be provided with a written informed consent document which specifies the risks and confidentiality protections and limits of study procedures.

Risks associated with EMA: Risks associated with the EMA portion of the study are minimal and include potential loss of confidentiality (described previously) and the potential for surveys to prompt participants at a time when it is inconvenient or unsafe from them to complete a survey (i.e., while driving). Participants will not only provide

their preferred time window for morning reports, but will also be provided with a time window for completing reports to minimize this risk. They are also informed that some missed sessions are expected and that they are not penalized for a few missed sessions. Participants are asked to sign an agreement stating that they will not complete a session while driving or in any other situation where it is potentially unsafe to do so. The EMA assessments do not provide a method of communicating with research staff in real time. Participants will be informed that study staff will not receive EMA responses in real time and thus it is not a method to communicate directly with the study team or receive assistance. All participants will be provided with a variety of community referrals prior to the start of the EMA component of the project.

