Security of Remote Data Storage Cloud including Physiology and Geolocation. This project will use a cloud-based smartphone application provided by Ilumivu, Inc. in a fee-for-service manner to collect remote ecological momentary assessment data. We will use the same platform through Ilumivu for physiological and geolocation data collected via wearable activity trackers. Participants will be informed of the specific data points that will be collected from their particular smartphone (or study smartphone) model and the activity tracker model. Study data will not be shared outside the study team or analyzed for reasons outside the scope of this research project. In addition, the Ilumivu application system allows specific security measures including requiring a user identification and password. The core system implements a hierarchical, roles-based security model that determines access to information and system capabilities. Data files are stored in a secure database and never on the server's file system. Data can be stored in either an encrypted manner or in clear-text. Secure Sockets Layer (SSL) protocols are also implemented using the client's certificate or one acquired by Ilumivu on behalf of its user. All data are encrypted in transmission.

Safety and Monitoring Plan. A procedure for clinical deterioration has been established based upon our experience with previous and ongoing NIH-funded clinical trials. All investigators and study staff will be instructed to use their best clinical judgment regarding emergencies and inform the PI as soon as possible. In addition to relying on clinical judgment on the part of the licensed providers on this team who are experienced with this population, we will also monitor alcohol and drug use, depression, and IPV using standardized measures (TLFB, BDI-II, CTS-2, breathalyzer tests and urine drug screens) in order to detect any symptom worsening requiring further evaluation. Additionally, participants will be advised to observe any signs of worsening alcohol use, depression symptoms, or aggression, and to discuss these challenges with study staff.

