**Suicide Specific Risk Identification and Response Plan.** Specific precautions will be taken to prevent harm to participants and potential participants. Project staff will be supervised by [name] (PI), and Drs. [name] and [name] (local Co-Is), who are licensed psychologists. All project staff will be specifically trained to assess suicide risk, including ideation, plan, and intent as well as history of ideation or attempts, and they will be trained to develop a safety contract with participants. In initial screening procedures, participants identified by clinical interview with both suicidal ideation and acute intent will be excluded from the study, but will be offered emergency psychiatric care. This care is available 24 hours per day at MUSC, as indicated above. In addition to the assessment measures specified in the Research Plan, the Beck Depression Inventory-II will be administered. Any participant any participant scoring above 25 on the BDI-II (administered at each visit) or answering a "1" or above to question 9 will be specifically queried about suicidal ideation and intent. In any instance where ideation or intent is identified, the PI will be immediately notified and will contact the participant for further evaluation. If both ideation and intent are present, the aforementioned hospital intervention will be provided. Thus, all assessment points represent suicide risk identification, assessment, and intervention opportunities. Study staff will be specifically trained regarding the increased risk of suicide in Veterans, and will receive specific instruction of suicide risk assessment, should a Veteran be enrolled.

All telehealth participants complete a participant locator form with study staff, that allows the study team to identify local emergency care facilities and contact information. Specifically, for out of state or remote participants, the study staff will compile a list of referrals and emergency contacts to provide to study participants ahead of enrollment. Ahead of appointments that are taking place outside of the Charleston area (both in SC and outside of SC), the study team will ensure a local (to participant) emergency line has been identified. In the event of a true emergency, the study team can contact the local authorities or emergency dispatch to send help to participant.

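### The suicide-risk plan relies on a BDI-II at every visit, but Table 1 schedules it at baseline only, and the documents do not say which prevails

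*Combined protocol and SAP*

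**What the plan says.** Three places in the combined protocol and SAP deal with the timing of the BDI-II.

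- **Suicide Specific Risk Identification and Response Plan (section 2).** Staff must ask about suicidal ideation and intent for anyone "scoring above 25 on the BDI-II (administered at each visit", or anyone who rates item 9 at 1 or more. The next step is explicit: "In any instance where ideation or intent is identified, the PI will be immediately notified and will contact the participant for further evaluation". The plan then claims full coverage: "Thus, all assessment points represent suicide risk identification, assessment, and intervention opportunities".
- **Safety and Monitoring Plan (section 2).** Alcohol and drug use, depression and IPV are to be monitored "using standardized measures (TLFB, BDI-II, CTS-2, breathalyzer tests and urine drug screens) in order to detect any symptom worsening requiring further evaluation".
- **Table 1.** The row "Beck Depression Inventory-II (BDI-II)" has a mark under baseline and none under Exit or Daily.

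A visit after baseline does exist. The section on HRV-B usability describes what participants do there: "In addition to providing subjective usability, feasibility, and acceptability at the exit interview", they complete three further questionnaires. The Assessment Procedures paragraph in section 2 also refers to exit interview procedures.

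**The concern.** The safety text and the visit schedule give different instructions. Staff who follow the suicide plan would give the BDI-II at exit. Staff who build visit packets or REDCap forms from Table 1 would not. In that second case two safety provisions stop working after baseline: the score and item 9 trigger has nothing to act on, and the check for worsening depression has only one score.

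The eligibility and withdrawal rules make this matter more. The exclusion criterion requires suicidal ideation together with intent, and the suicide plan describes screening in the same terms, so a person with ideation alone can enroll. The withdrawal rules in section 2 include active ideation arising during the study, and they work only if ideation is noticed after baseline. Ideation that is new or worse since baseline, and not volunteered, could pass through the exit visit without the query and PI contact that the suicide plan promises.

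Daily EMA does not replace the screen. It collects mood and affect, but the section on potential risks states: "Participants will be informed that study staff will not receive EMA responses in real time".

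**Working it through.** There is no figure in the plan to reproduce. The check is a row-by-row reading of Table 1 against the safety text.

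**Step 1. Visits at which the BDI-II is required.** Table 1 has two visit columns, Baseline and Exit, plus Daily.

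| Source | Baseline | Exit | Visits covered |
|---|---|---|---|
| Suicide plan (each visit) | yes | yes | 2 of 2 |
| Table 1 | yes | no | 1 of 2 |

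With 100 participants and full attendance, the suicide plan implies 100 × 2 = 200 BDI-II forms and Table 1 implies 100 × 1 = 100. The difference, 200 − 100 = 100, is the whole set of exit forms. It counts forms, not missed cases; the documents give no rate of positive screens.

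**Step 2. Whether another exit instrument fills the gap.** The instruments marked at Exit are the locator form, Adverse Events Form, TLFB, CTS-2, short Dyadic Adjustment Scale, WAMMI, PSSUQ and CSQ. That is 8 instruments, of which 0 measure depression or suicidality.

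**Step 3. Whether the blank could be an error in reading the table.** Rows with two marks survive intact: the TLFB, the "Revised Conflict Tactics Scale" and the Dyadic Adjustment Scale each show baseline and Exit. Rows marked only at Exit, such as the Adverse Events Form and WAMMI, show the mark in the right column. The single mark in the BDI-II row therefore appears to be what the table says.

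**Step 4. The five monitoring tools named in the Safety and Monitoring Plan.**

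| Tool | Baseline | Exit |
|---|---|---|
| TLFB | marked | marked |
| CTS-2 | marked | marked |
| BDI-II | marked | blank |
| Breathalyzer | marked | blank |
| Urine drug test | marked | blank |

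Three of the five are marked at baseline only. By domain, alcohol and drug use is still repeated through the TLFB, and IPV through the CTS-2. Depression is the one domain of the three with no repeated measure in Table 1.

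**Step 5. Whether the documents rank the two sources.** They do not. The suicide plan introduces the BDI-II as an addition to the Research Plan measures, which could place it outside Table 1. Yet Table 1 lists it with its own purpose and visit. The title of Table 1 mentions only eligibility and baseline, but the table also schedules Exit and Daily measures, so the title does not explain the blank.

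**The case against.** The best reply is that Table 1 is incomplete and the suicide plan is the operative text. There is evidence for this. The Telehealth section requires a saliva alcohol test at each visit in place of the breathalyzer, yet the alcohol-screen row of Table 1 is also marked at baseline only. So at least one other each-visit procedure has no Exit mark. On this reading the BDI-II is given at exit and the table lacks one mark. That reading is plausible and may be what was meant, but nothing in the documents establishes it, and a site working from the table would not know.

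The remaining safeguards are also real. All project staff are trained to assess ideation, plan and intent. Adverse events, defined to include unwanted psychological change, are to be identified at study visits and interviews and reviewed weekly by the PI and Study Physician. Participants are told to raise worsening symptoms. These narrow the consequence. None is a structured screen, and each depends on disclosure or on a staff member's judgment.

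Three stronger inferences are tempting and are not supported:

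- **That the exit visit has no depression or suicide screen.** This holds only if Table 1 overrides the suicide plan.
- **That the blank is peculiar to the BDI-II and therefore deliberate.** The breathalyzer and urine rows have the same blank.
- **That the DSMB would lose a depression score it was due to receive.** Section 3 gives it participant safety, adverse events and data integrity; nothing sends it BDI-II scores.

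**Conclusion.** The inconsistency stands. The suicide plan requires the BDI-II at 2 of 2 scheduled visits and Table 1 provides it at 1 of 2. The consequence is conditional. If forms follow Table 1, the suicide trigger works only at baseline, worsening depression cannot be measured with the named tool, and 0 of the 8 exit instruments cover depression or suicidality. If the suicide plan governs, the defect is a missing mark in a table. The documents do not decide between these.

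The conclusion assumes that baseline and exit are the only scheduled visits, as Table 1 shows. It makes no claim about how many at-risk participants would be missed. The point should be corrected because it concerns a stated safety commitment in a sample that may include people with ideation at entry.

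**What to change.** Mark the BDI-II at Exit in Table 1. In the suicide plan, replace the each-visit wording with a statement that the BDI-II is given at baseline and at the exit visit, and that the total-score and item 9 trigger applies at both. The Safety and Monitoring Plan then has the second score it needs and requires no edit for depression.

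If baseline only is intended, the safety text should change instead: remove the each-visit wording and the all-assessment-points claim, take the BDI-II out of the list of tools for detecting worsening, and say how suicide risk is assessed at exit.

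The first option costs one mark, one sentence, one more short questionnaire per participant at exit, and staff time to follow up positive screens as participation ends. The suicide plan already provides for staff training, PI contact and local emergency contacts.

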### 3. Provisions to Monitor the Data to Ensure the Safety of Subjects

Trial Management. [name] (PI) will be responsible for monitoring the trial. The study will be managed from the Addiction Sciences Division within the Department of Psychiatry and Behavioral Sciences at the Medical University of South Carolina (MUSC), College of Medicine, Charleston, SC.

Responsible Party. [name] (PI) will be responsible for distinguishing between serious (SAEs) and non-serious adverse events (AEs), and determining study relatedness.

DSM Board. We will create a DSMB to monitor overall participant safety, the rate and severity of adverse events, and the validity and integrity of the data. The panel will include 2 researchers with experience in treating patients with AUD and a biostatistician. The board may be called at any point if needed for unexpected AEs, etc. Modifications will be made in the procedures and/or the protocol if necessary based on the recommendations of the board. Confidentiality will be maintained during all phases of the study.

Adverse Events. An *Adverse Event (AE)* is defined as any unwanted change, physically, psychologically or behaviorally, that occurs in a study participant during the course of the study that may or may not be related to study participation. AEs are reportable to the local Institutional Review Board (IRB) if the AE is unexpected AND related or possibly related AND serious or more prevalent than expected. The IRB definition of *unexpected* is that the AE is not identified in nature, severity or frequency in the current protocol, informed consent, investigator brochure or with other current risk information. The definition of *related* is that there is a reasonable possibility that the adverse event may have been caused by the drug, device or intervention. All AEs will be reviewed by the PI, and annually by the Data and Safety Monitoring Board (DSMB) and MUSC IRB. A *Serious Adverse Event (SAE)* is defined as an adverse event that has one of the following outcomes: results in death, is life-threatening, requires inpatient hospitalization or prolongation of existing hospitalization, results in persistent or significant disability/incapacity, is a congenital anomaly/birth defect, OR requires intervention to prevent one of the above outcomes.

AE/ Unanticipated Problem Follow-up. Unanticipated problems, potential AEs and SAEs will be identified during the study visits and interviews. All unexpected AEs and SAEs will be monitored until resolved. A detailed summary of all AEs will be prepared weekly by the research staff and reviewed by the PI and Study Physician at the weekly study team meeting.

Safety Reporting. All unexpected AEs will be reported to the MUSC IRB and NIH within 10 working days. AEs are reportable if the AE is unexpected AND related or possibly related AND serious or more prevalent than expected. SAEs will be reported within 48 hours of knowledge of the SAE. In accordance with the MUSC IRB, any deaths that occur during the study or 30 days post termination from the study will be reported within 24 hours, regardless of whether it is expected or unrelated. Follow-up of all unexpected and serious AEs will also be reported to the appropriate agencies. All AEs are reviewed by the PI, and annually by the DSMB and IRB. Any significant actions taken by the local IRB and protocol changes will be reported to NIAAA. An annual report summarizing all AEs will be provided to the NIAAA project officer. This report will include 1) confirmation of adherence to the DSMP, 2) a summary of any data and safety monitoring issues that have arisen since the previous report, 3) a description of any changes in the study protocol or DSMP that might possibly affect risk, and 4) all new and continuing IRB approvals.

